1.0 Introduction and Background

In 2011, liposomal bupivacaine received FDA approval for the use of local surgical site infiltration, and its use has become common for a variety of abdominal, gynecological, and orthopedic surgeries, with varying efficacy.^{1,2,3} Studies evaluating the efficacy of liposomal bupivacaine for regional procedures have also displayed mixed results.⁴

Liposomal bupivacaine has recently been approved by the FDA for use in brachial plexus blocks for patients undergoing major shoulder surgery.⁵ Per the manufacturer's data, ISB using liposomal bupivacaine provided significant pain reduction in the first 48 hours after surgery compared to ISB using placebo, establishing that liposomal bupivacaine has an opioid sparing effect in this patient population without significant risk.

A recent study compared the addition of liposomal bupivacaine to plain bupivacaine for interscalene blocks in patients undergoing shoulder surgery, and found a modest improvement in pain.⁶

At a cost of about \$300 per administration for liposomal bupivacaine, there are significant economic impacts to be considered, given that plain bupivacaine is significantly less expensive. Data from future studies are required to perform a cost-benefit analysis for this new drug.

Common and relatively inexpensive adjuvants have been shown to extend the duration of analgesia provided by interscalene nerve blocks (ISB) using plain bupivacaine, with a significant analgesic effect extending up to 48 hours postoperatively.⁷⁻⁹

To date, there has been no study comparing the efficacy of ISB using liposomal bupivacaine vs plain bupivacaine with these common adjuvants, such as epinephrine, dexamethasone, clonidine, and buprenorphine.

The purpose of this study is to determine whether the use of plain bupivacaine with common adjuvants for ISB provides non-inferior analgesic results compared to the use of liposomal bupivacaine for ISB, in patients undergoing primary total shoulder arthroplasty.

LB= Liposomal bupivacaine

PBA= Plain bupivacaine + adjuvants

ISB= Interscalene peripheral nerve block

Single Injection interscalene brachial plexus nerve block with adjuvants vs. Liposomal bupivacaine
interscalene brachial plexus nerve block for total shoulder arthroplasty

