5.2 Treatment Administration

Patients assigned to the ISB with liposomal bupivacaine group will receive a 20cc solution of 133mg liposomal bupivacaine (10mL expanded with 10mL 0.25% plain bupivacaine) in an interscalene block, conducted via Ultrasound guidance.

Patients assigned to the ISB with plain bupivacaine and adjuvants group will receive a 20cc solution of plain bupivacaine 0.25% with adjuvants (clonidine 1.6mcg/mL, epinephrine

Single Injection interscalene brachial plexus nerve block with adjuvants vs. Liposomal bupivacaine interscalene brachial plexus nerve block for total shoulder arthroplasty

2.5mcg/mL, dexamethasone 0.1mg/mL, and buprenorphine 150mcg) in an interscalene block, conducted via Ultrasound guidance.

The absolute dosages of medications will be as follows: either 133mg liposomal bupivacaine with 25mg plain bupivacaine OR 50mg plain bupivacaine with adjunct medicines: 32mcg clonidine, 50mcg epinephrine, 2mg dexamethasone and 150mcg buprenorphine.

The treatment will be administered by either an attending anesthesiologist, or a resident anesthesiologist under the supervision of an attending.

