6.1 Analysis of Primary Objective

6.1.1 The VAS-NRS scale is an 11-point scale that assesses pain from 0- “No pain” to 10- “Worst possible pain”. For this study, a difference of ≥ 2 points will be considered to be clinically significant. Pain scores will be taken measured on departure from the PACU and at each 12-hour interval, and average pain scores for each cohort will be calculated. The area under the curve (AUC) for each cohort will be calculated using the least squares method. The inferiority threshold will be set as ≥ 2 points over 48 hours, which would result in an AUC difference of 96 point-hours.

Prior studies have found an AUC48 for ISB using liposomal bupivacaine to be 136.4 with a standard error of 12.09.¹⁰ There are no data evaluating the AUC48 for ISB using plain bupivacaine with adjuvants; however we estimate that the

Single Injection interscalene brachial plexus nerve block with adjuvants vs. Liposomal bupivacaine interscalene brachial plexus nerve block for total shoulder arthroplasty

pain scores will be within 20% of that of liposomal bupivacaine, resulting in an AUC48 of 163.0 or below, and a similar standard error of 12.09.

With a 2-sample t test using $\alpha = 0.05$ and $\beta = 0.1$, the study will be powered to detect a difference of 96 point-hours between the 2 groups with 36 subjects per arm.

To test for differences in these AUC between the 2 arms, an independent t-test will be used; if the observed p-value is <0.05 , statistical significance will be assumed. Two-sided t-test will be performed for statistical analysis once data collection is complete.

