Appendix H- Data Collection Form

| | |
|--------------|-----------------------------------------|
| | Assigned Study Number: |
| | WakeOne MRN |
| Demographics | Age |
| | Sex |
| Procedure | Comorbidities |
| | Pre-surgical analgesics |
| Medical Hx | Preop pain score |
| | Pre-op multimodal analgesics |
| | Post-Block assessment |
| Pre-Op | Intra-op Narcotics (PO oxy equivalents) |
| | Pain score in PACU p/t discharge |
| Intraop | PACU block assessment |
| | PACU opioids (PO oxy equivalents) |
| | +6hr worst pain score (VAS) |
| PACU | |
| | |

Single Injection interscalene brachial plexus nerve block with adjuvants vs. Liposomal bupivacaine interscalene brachial plexus nerve block for total shoulder arthroplasty

| | |
|------------------|-----------------------------------------------------------------------------------------------------------------------------------------------------------------------------------------------------------------------------------------------------------------------------------------------------------------------------------------------------------------------------------------------------------------------------------------------------------------------------------------------------------------|
| | 
+12h worst pain score (VAS)
 
+24h worst pain score (VAS)
 
+36h worst pain score (VAS)
 
+48h worst pain score (VAS)
 
+6hr opioid use (PO oxy eq)
 
+12h opioid use (PO oxy eq)
 
+24h opioid use (PO oxy eq)
 
+36h opioid use (PO oxy eq)
 
+48h opioid use (PO oxy eq)
 
Likert Satisfaction #1
 
Likert satisfaction #2 Nonopiod Analgesics Used Side effect evaluation (Itching, Nausea/vomiting)
 |
| Post OP | |
| Off study | 
("OFF" if applicable)
 
Reasons:
 |

Date of study completion:

Evaluable subject?

Protocol deviations?

Single Injection interscalene brachial plexus nerve block with adjuvants vs. Liposomal bupivacaine interscalene brachial plexus nerve block for total shoulder arthroplasty

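### The primary analysis tests AUC48 against zero, names no analysis set and ignores the recorded block assessments, so the non-inferiority question has no decision rule and no check on failed blocks

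*Combined protocol and SAP*

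**What the plan says.** Section 1.0 gives the purpose: to find out whether plain bupivacaine with adjuvants "provides non-inferior analgesic results compared to the use of liposomal bupivacaine for ISB". Section 6.1.1 sets the margin: "The inferiority threshold will be set as ≥ 2 points over 48 hours, which would result in an AUC difference of 96 point-hours".

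The analysis in the same section is a test of difference: "To test for differences in these AUC between the 2 arms, an independent t-test will be used", with significance at p < 0.05, and "Two-sided t-test will be performed for statistical analysis once data collection is complete". Section 6 contains no confidence-limit rule against 96, no definition of who enters the comparison, and no sensitivity analysis.

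The data collection form in Appendix H has a "Post-Block assessment" before surgery and a "PACU block assessment" after it, and asks whether the subject is evaluable and whether there were protocol deviations. None of these fields is defined, and Section 6 uses none of them. On operators, section 5.2 says: "The treatment will be administered by either an attending anesthesiologist, or a resident anesthesiologist under the supervision of an attending". It requires ultrasound guidance in both arms. Section 7.0 keeps patients in follow-up but does not say who is analysed.

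**The concern.** A non-inferiority claim needs a rule that compares the plausible size of the difference with the margin. A t-test against zero does not supply one: p ≥ 0.05 does not show that the difference is below 96, and p < 0.05 does not show that it is above.

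Once such a rule exists, failed blocks matter in a way they would not in a superiority trial. A block that misses its target leaves the patient in pain whichever solution was injected. If this happens about equally often in both arms, those patients contribute almost no difference and the arms move together. In a superiority trial that is conservative. Against a margin, it makes it easier to call a mixture non-inferior when it would be worse by the full margin in working blocks. The form already has fields that could help a reader tell similar solutions from shared technical failure, but the plan leaves them out of the analysis.

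**Working it through.** **Inputs from the documents.** Margin 2 × 48 = 96 point-hours (6.1.1). Liposomal mean AUC48 136.4, SE 12.09; expected comparator mean 163.0, so an expected difference of 163.0 − 136.4 = 26.6 (6.1.1). 36 per arm (6.1.1, 6.3).

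**Assumptions.**
- AUC SD: not stated. Section 6.2.1 gives SD 2.88 and SE 0.36 for the 48-hour score; 2.88/0.36 = 8 implies n = 64. If the AUC came from the same patients, SD = 12.09 × 8 = 96.7.
- Failed-block mean AUC: not stated. The 5.5 in 4.2.1.2 gives 5.5 × 48 = 264. That score is a 48-hour mean after a plain-bupivacaine block, so it is only a proxy. I also ran 3.8 × 48 = 182.4 and 8 × 48 = 384.
- Failure share f: not stated. Shown from 0 to 20%, equal in both arms.

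**The plan's own sample size.** n per arm = 2(1.96 + 1.2816)² × 96.7² / 96² = 21.3, so 22 at 90% power, not 36. Reaching 36 needs an SD of about 125.6, so I ran that SD too.

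**Dilution formulas.** With working-block mean m and failed-block mean F in an arm:
- arm mean = (1 − f)m + fF
- arm variance = SD² + f(1 − f)(m − F)²
- difference between arms = (1 − f) × working-block difference
- chance that the upper 95% limit is below 96 = Φ[(96 − difference)/SE − 1.96], with SE = √[(sum of the two variances)/36].

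**Worked case: f = 10%, working-block difference 96.**
- Liposomal arm: mean 0.9 × 136.4 + 0.1 × 264 = 149.16; variance 9350.9 + 0.09 × 127.6² = 10816.2.
- Comparator arm: mean 0.9 × 232.4 + 0.1 × 264 = 235.56; variance 9350.9 + 0.09 × 31.6² = 9440.8.
- Difference 86.4; SE = √(20257.0/36) = 23.7; Φ(9.6/23.7 − 1.96) = 6.0%.

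| f | Diluted difference (from 96) | Chance of upper limit < 96, SD 96.7, F = 264 | Range over F = 182.4 to 384 and SD 96.7 or 125.6 | Same chance at working-block difference 26.6 (SD 96.7, F = 264) |
|---|---|---|---|---|
| 0 | 96.0 | 2.5% | 2.5% | 86.1% |
| 5% | 91.2 | 4.0% | 3.5–4.0% | 85.2% |
| 10% | 86.4 | 6.0% | 4.8–6.1% | 84.6% |
| 15% | 81.6 | 8.7% | 6.2–9.1% | 84.2% |
| 20% | 76.8 | 12.0% | 7.8–12.9% | 84.1% |

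Simulations with t quantiles agree: 2.4–2.5%, 3.8–3.9%, 5.6–5.9% and 8.1–8.7% at f = 0, 5, 10 and 15%.

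**The test as written.** If p ≥ 0.05 were read as similar, its chance at a working-block difference of 96 (SD 96.7, F = 264) rises from 1.2% to 2.5%, 4.6% and 11.8% at f = 5, 10 and 20%.

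**Sensitivity.**
- Unequal failure changes the dilution. Failures of 5% liposomal and 15% comparator leave a difference of 94.4; the reverse leaves 78.4.
- At 26.6 and SD 96.7 the result depends on F. With f = 20% the chance is 65% at F = 384 and 90% at F = 182.4, against 86% without failures.

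**The case against.** The strongest reply is that the target is the block as delivered. Sections 1.0 and 2.1 ask about patients having surgery, not about patients whose block worked. With 10% failures in each arm the true all-patient difference is 86.4, which is below 96, so a non-inferior conclusion is correct for that target. The percentages are errors only for the working-block effect. This stands. It is why all randomised patients should be the main set and the working-block result only supportive.

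The percentages also use a confidence-limit rule that the plan does not contain. That stands too, and the missing rule is the more basic gap.

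Three stronger readings are tempting and not supported:
- A reader might infer that the plan analyses all patients. No analysis set is named, and the undefined evaluability field would also allow failed blocks to be dropped.
- A reader might infer that failed blocks generally favour non-inferiority. They also add variance. At 26.6 the chance falls slightly under the main assumptions and rises only if failed-block pain is close to that of working blocks. At that difference a non-inferior conclusion would be right anyway.
- A reader might infer that success should be required in both sets. Block success is observed after randomisation, and section 5.2 gives 25 mg plain bupivacaine in one arm and 50 mg in the other, so early success could differ by arm and bias the subset either way. In simulation at 26.6, requiring both sets also lowers power from about 85% without failures to about 78% at 10% failures and 75% at 15%.

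Nor do the documents show that blocks will fail often, or that supervised residents cause failures.

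**Conclusion.** The concern holds in limited form. From the text alone, section 6.1.1 gives no rule that answers the non-inferiority question, no analysis set, and no use of the block assessments. The size of the dilution is conditional: with equal failure shares of 5 to 15% and a working-block difference at the margin, the chance of an upper limit below 96 goes from 2.5% to roughly 4 to 9%. The direction at the margin holds across the SDs and failed-block means tried. The size rests on an inferred SD, a proxy for failed-block pain, and an assumed, equal failure rate. It does not show that the trial is likely to reach a wrong conclusion if the true difference is near the expected 26.6. The change is worth making because it is cheap and section 6.1.1 itself says there are no AUC48 data for the adjuvant mixture.

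**What to change.** In section 6.1.1:
1. Name all randomised patients, in their assigned arms, as the main analysis set.
2. State the rule: conclude non-inferiority only if the upper limit of the two-sided 95% CI for the AUC48 difference (plain bupivacaine with adjuvants minus liposomal bupivacaine) is below 96 point-hours.
3. Add a pre-specified supportive, non-gating analysis: the same difference and CI in patients who received the assigned block and had a working block at the pre-surgery assessment. The investigators should define the criterion, and what the form must record to apply it, before unblinding.
4. Report failed blocks by arm, and discuss any disagreement between the two sets when interpreting the result.

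The cost is some SAP wording, a defined form entry and one extra run. With 10% failed blocks, about 32 per arm remain in the supportive set. At SD 96.7 and a difference of 26.6, its chance of an upper limit below 96 is about 82%, against 86% with 36. Because that set is formed after randomisation and block success may depend on arm, it cannot replace or gate the main analysis.

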6.2 Analysis of Secondary Objectives

- 6.2.1 For the mean VAS-NRS score at 48 hours, prior studies have found an average score of 3.8 with a standard deviation of 2.88 (standard error of 0.36) for ISB using liposomal bupivacaine.¹⁰ There have been no studies to evaluate the pain scores after ISB using plain bupivacaine with adjuvants. This study will be powered to detect a difference of at least 0.4 on the VAS-NRS scale. We will define the threshold for inferiority as a difference of ≥ 2 points on the VAS scale. Analysis will be conducted using a two-sample t test with $\alpha = 0.05$ and $\beta = 0.1$.
- 6.2.2 For the comparison of post-operative opioid consumption, each patient's total post-operative opioid usage during the first 48 hours will be converted to oxycodone equivalents. The geometric mean opioid consumption for each cohort will be calculated, and the two cohorts will be compared for statistical difference using a two-sample t test, with $\alpha = 0.05$ and $\beta = 0.1$.
- 6.2.3 Patient satisfaction will be assessed on POD#2 by 5-point Likert rating scale, and via a binary question of "would you recommend this pain relief regimen to the next patient". The results of these questions will be compared with a Fisher's Exact Test, with $\alpha = 0.05$.

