4.2 Secondary Outcomes

- 4.2.1 Mean VAS-NRS pain score at 48 hours.
 - 4.2.1.1 For patients undergoing ISB with liposomal bupivacaine, the mean VAS pain score at 48 hours was 3.39 with a standard error of 0.37.¹⁰
 - 4.2.1.2 There are no existing data to predict the mean VAS pain score at 48 hours for patients undergoing ISB with plain bupivacaine + adjuvants, however a similar study using plain bupivacaine alone demonstrated a mean NRS (similar to VAS) pain score of 5.5 with standard error +/-0.5⁶. We expect the mean pain score to be slightly below this value, approximately 4.5.
- 4.2.2 Postoperative opioid consumption
 - 4.2.2.1 The mean rescue opioid consumption (in IV morphine equivalents) in the first 48 hours after receiving ISB using liposomal bupivacaine was 12.0 +/- 2.3 in a previous study.¹⁰
 - 4.2.2.2 We expect the patients treated with plain bupivacaine and adjuvants to use a similar average of 12.0 intravenous morphine equivalents in the first 48-hours following surgery. For the purpose of this study, we will convert IV morphine equivalents to oral codeine equivalents.
- 4.2.3 Satisfaction with surgical experience
 - 4.2.3.1 At the 48 hour mark, the patient's satisfaction with the surgical experience, satisfaction with pain control, and willingness to recommend the procedure to another patient will be assessed via Likert scale. Adverse events will also be evaluated.

Single Injection interscalene brachial plexus nerve block with adjuvants vs. Liposomal bupivacaine interscalene brachial plexus nerve block for total shoulder arthroplasty

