6.3 Power and Sample Size

We will have a power of 80%, as described in 10.1.1, with a sample size of 36 patients in each arm for a total of 72 patients, plus 8 patients to allow for attrition, for a total of 80 patients.

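### Section 6.2.1 claims power for a 0.4-point difference at 48 hours, but 36 per arm gives about 9%; sections 6.1.1 and 6.3 give 90% and 80% power for the same 36 per arm

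*Combined protocol and SAP*

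**What the plan says.** **48-hour score (section 6.2.1).** The variability is taken from a cited study: "prior studies have found an average score of 3.8 with a standard deviation of 2.88 (standard error of 0.36". The plan then states "This study will be powered to detect a difference of at least 0.4 on the VAS-NRS scale", sets the inferiority threshold at 2 points, and names a two-sample t test with alpha 0.05 and beta 0.1. It gives no sample size of its own for this endpoint.

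**Primary outcome (section 6.1.1).** Beta is set at 0.1 and alpha at 0.05, and the claim is: "the study will be powered to detect a difference of 96 point-hours between the 2 groups with 36 subjects per arm". On sidedness: "Two-sided t-test will be performed for statistical analysis once data collection is complete".

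**Sample size (section 6.3).** "We will have a power of 80%, as described in 10.1.1, with a sample size of 36 patients in each arm". Eight patients are added for attrition, making 80 in total.

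**Expected 48-hour scores (section 4.2.1).** Citing the same reference as 6.2.1, for liposomal bupivacaine "the mean VAS pain score at 48 hours was 3.39 with a standard error of 0.37". For plain bupivacaine with adjuvants: "We expect the mean pain score to be slightly below this value, approximately 4.5".

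**The concern.** A difference of 0.4 points is about one seventh of the printed SD (0.4 / 2.88 = 0.14). A trial of 36 per arm cannot reliably detect an effect that small, so the power statement looked wrong on sight.

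Pain at 48 hours is a stated secondary objective (2.2.1), and the trial hypothesises similar pain relief in the two arms. A reader who trusts 6.2.1 could take a non-significant 48-hour result as evidence against any difference of 0.4 points or more. If the true difference were 0.4, the trial would miss it about 91% of the time, and that misreading would favour the study hypothesis.

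For the primary outcome, 6.1.1 and 6.3 together leave the reader unable to tell which power the 36 per arm was set for, or with what SD.

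**Working it through.** **Inputs**

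| Input | Value | Source |
|---|---|---|
| SD, 48-hour score | 2.88 | 6.2.1 |
| Difference to detect | 0.4 points | 6.2.1 |
| Inferiority threshold | 2 points | 6.2.1 |
| Alpha, beta | 0.05, 0.1 | 6.2.1 |
| Patients per arm | 36 (40 with no attrition) | 6.1.1, 6.3 |
| Sidedness | two-sided | 6.1.1; assumed to apply to 6.2.1, which states none |

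Power is computed from the noncentral t distribution with 2n − 2 degrees of freedom and noncentrality δ / (SD × √(2/n)).

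**1. Power for 0.4 points**

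- Standard error of the difference: 2.88 × √(2/36) = 0.679.
- Noncentrality: 0.4 / 0.679 = 0.589. The critical value is t(0.975, 70) = 1.994.
- Power: **8.95%**. With 40 per arm it is 9.4%. One-sided at 0.05 with 36 per arm it is 14.4%.
- The stated 90% is therefore not reproduced. The 80% of section 6.3 is not reached either.

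**2. What 0.4 points would need**

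- Normal formula, n per arm = 2 × SD² × (z for alpha + z for power)² / δ².
- 90%: 2 × 2.88² × (1.960 + 1.282)² / 0.4² ≈ 1,090 (1,091 by exact t).
- 80%: the same formula with 0.842 gives 814 (815 by exact t).
- At 36 per arm, the SD would have to be 0.52 for 90% power, or 0.60 for 80%.

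**3. What 36 per arm can show at 48 hours (two-sided 0.05)**

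- 95% confidence interval half-width: 1.994 × 0.679 = 1.35 points.
- Detectable difference: 2.23 points at 90% power and 1.93 at 80%.
- Power for 2 points: 82.8%.

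**4. Reading 0.4 as the true difference against the 2-point margin**

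The distance to the margin is 2 − 0.4 = 1.6 points. Power is 64% at one-sided 0.025 and 75% at one-sided 0.05. Both are below 80%.

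**5. The two 48-hour baselines**

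Against the expected 4.5, the difference is 4.5 − 3.39 = 1.11 (power 36%) or 4.5 − 3.8 = 0.70 (power 17%). The 0.4 corresponds to neither.

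**6. Primary outcome: 90% or 80%**

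- The 96 point-hours is 2 points × 48 hours.
- At 36 per arm, two-sided 0.05, a power of 90% implies an AUC SD of 124 and a power of 80% implies 143.
- If 36 per arm gives 80% (SD 143), then 90% needs 48 per arm. The two statements cannot both hold for one test with one SD.
- The plan prints only a standard error of 12.09 for the AUC, with no SD and no source sample size. **Assumption:** the source n is 64, borrowed from (2.88 / 0.36)² in 6.2.1. Then SD = 12.09 × 8 = 96.7, and power for 96 point-hours is 98.6%. For an assumed source n of 50 to 80 it runs from 99.7% down to 96.0%. Neither stated power is reproduced, but nothing here shows the stated primary test to be underpowered.
- Illustration only: as a non-inferiority test with margin 96 and true difference 163.0 − 136.4 = 26.6, SD 96.7 gives 85% at one-sided 0.025 (77% to 92% over the same range of source n) and 91.5% at one-sided 0.05.

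**The case against.** The strongest reply is that 36 per arm does fit 6.2.1 once the 2-point threshold in the next sentence is used. With margin 2, true difference 0, SD 2.88, one-sided alpha 0.05 and 90% power, the normal formula gives 2 × 2.88² × (1.645 + 1.282)² / 2² = 35.5, so 36 per arm (89.8% by exact t). On that view 0.4 is a stray figure, beta 0.1 is right, and deleting beta removes something correct. The arithmetic stands and may explain where 36 came from, but that is inference. It is power for 2 points, not 0.4, and it needs a one-sided 0.05 test that the plan does not state. At two-sided 0.05, or equivalently a 2-point margin at one-sided 0.025 with no true difference, power is 82.8%. So 83% is the figure the stated test supports on either reading.

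Other points stand in part:

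- Beta 0.1 is in the analysis sentence of 6.2.1, not in the 0.4 sentence. It is still the only power given for that endpoint, and 80% fails too.
- Section 6.3 names no endpoint, so that it restates the 6.1.1 calculation is likely rather than certain.
- The 90% in 6.1.1 is roughly recovered (91.5%) under a one-sided 0.05 non-inferiority reading with the assumed SD. The section states neither that test nor that SD.
- The 3.39 versus 3.8 mismatch hardly affects power: an SD of 0.37 × 8 = 2.96 gives 8.7% for 0.4 points. A detectable difference also need not equal the expected one. This part is a matter of consistency only.

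**Conclusion.** The concern holds. The 0.4-point statement is wrong on the plan's own figures: about 9% power against the implied 90%, with roughly 30 times the planned sample needed (1,091 / 36). This rests only on the printed SD, alpha and sample size, plus the two-sided test carried over from 6.1.1; a one-sided test raises the power only to 14%. The primary-outcome power is stated as 90% in one place and 80% in another for the same 36 per arm, with a dead cross-reference and no SD from which to settle it. The differing 48-hour inputs are a minor inconsistency.

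The sample size itself is not challenged. The AUC figures depend on an assumed source n and serve only to show that the stated primary test is not demonstrably underpowered. This should be fixed, but it does not threaten the trial.

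**What to change.** Keep 36 per arm and correct the statements.

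- **6.2.1:** delete the 0.4-point sentence and the beta of 0.1. In their place write: with SD 2.88 and a two-sided 0.05 test, 36 per arm has 83% power for a 2-point difference; the detectable difference is about 2.2 points at 90% power and 1.9 at 80%. If the sponsor in fact planned a one-sided non-inferiority calculation, it should say so and give the margin, assumed true difference and alpha.
- **6.1.1 and 6.3:** state one power in both places, with the SD, sidedness, margin and assumed true difference actually used. Replace the reference to 10.1.1 with the correct section.
- **4.2.1.1 and 6.2.1:** check the cited source and use one mean and one standard error.

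The cost is wording only: no extra patients and no change to the tests. The stated power for the 48-hour score becomes less favourable.

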Appendix E – Satisfaction Questionnaire

Subject Number: _____ DATE: ____ / ____ / ____ TIME: ____ : ____ AM/PM

Instructions: On the second day (48 hours) after surgery, please review the following questions, and choose the answer that best corresponds to each question regarding your experience.

| | Strongly Disagree | Disagree | Neutral | Agree | Strongly Agree |
|--------------------------------------------------------------------|----------------------|----------|---------|-------|-------------------|
| I believe my pain was well-controlled during after surgery. | | | | | |
| I would recommend this pain-control treatment to another patient. | | | | | |
| Have you had any itching since your surgery in your shoulder area? | YES | NO | | | |
| Have you had any nausea and/or vomiting since your surgery? | YES | NO | | | |

Single Injection interscalene brachial plexus nerve block with adjuvants vs. Liposomal bupivacaine
interscalene brachial plexus nerve block for total shoulder arthroplasty

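### Section 6.2.3 tests ordered 5-point satisfaction answers with Fisher's exact test, which is valid but ignores the order; a rank test with an effect estimate would usually serve better

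*Combined protocol and SAP*

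**What the plan says.** Section 6.2.3 describes two measures. The first is a rating: "Patient satisfaction will be assessed on POD#2 by 5-point Likert rating scale". The second asks whether the patient would recommend the regimen, and 6.2.3 calls that question binary. One rule covers both: "The results of these questions will be compared with a Fisher's Exact Test", at a significance level of 0.05. The section names no ordinal method, no rule for collapsing the five answers, no effect estimate and no expected distribution.

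Appendix E holds two agreement items: "I believe my pain was well-controlled during after surgery" and "I would recommend this pain-control treatment to another patient". Both sit under the same five columns, running from strong disagreement to strong agreement. The only yes/no items on that form concern itching and nausea or vomiting. Sections 4.2.3.1 and 5.1 also say that willingness to recommend is rated on a Likert scale, and Appendix H has two Likert satisfaction fields.

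Section 6.3 sets the size: "with a sample size of 36 patients in each arm for a total of 72 patients". Eight more are added as an attrition allowance, which brings recruitment to 80. That number was chosen for the pain AUC, not for satisfaction.

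**The concern.** The five answers are ordered, and the natural question is which arm is more satisfied. Fisher's exact test on a 2x5 table asks something broader: whether the two distributions differ in any way. It would return the same p-value if the five columns were shuffled. Two things follow.

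- Sensitivity to a consistent shift towards agreement or disagreement is spread over four degrees of freedom instead of being concentrated on one.
- The result is a bare p-value. A reader cannot see which arm did better, by how much, or what size of difference the data exclude.

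The second matters most if the result is not significant, because the plan offers no interval to show how little or how much that rules out.

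**Working it through.** There is no figure in the plan to reproduce: it states no power, effect size or answer distribution for satisfaction. The check therefore uses assumed distributions over a wide range.

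**Inputs from the plan.** 36 per arm (6.3), alpha 0.05 (6.2.3), five ordered categories (6.2.3, Appendix E).

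**Assumptions.**
- Two-sided testing; 6.2.3 does not state sidedness for this test.
- The Likert item is analysed as a 2x5 table, since no collapsing rule is given.
- Six baseline distributions, in % from strongly disagree to strongly agree: (20,20,20,20,20), (10,20,40,20,10), (5,10,20,40,25), (5,5,10,30,50), (2,3,5,25,65), (1,1,3,15,80).

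**Shift.** Under proportional odds, each cumulative odds P(Y≤k)/(1−P(Y≤k)) is multiplied by the OR. Example with (5,5,10,30,50) and OR 2:
- cumulative probabilities 0.05, 0.10, 0.20, 0.50
- odds 0.053, 0.111, 0.250, 1.000, doubled to 0.105, 0.222, 0.500, 2.000
- new cumulative probabilities 0.095, 0.182, 0.333, 0.667
- new distribution about (10, 9, 15, 33, 33)%

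**Simulation.** 2,500 trials per setting, so the Monte Carlo standard error is at most √(0.25/2500) = 0.01. Fisher's test in its 2x5 (Freeman-Halton) form, by full enumeration, is compared with the tie-corrected Wilcoxon rank-sum test. Relative loss = (Wilcoxon − Fisher)/Wilcoxon. Each column gives the range over the six baselines.

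| OR | Fisher power | Wilcoxon power | Relative loss |
|---|---|---|---|
| 2 | 0.16-0.21 | 0.23-0.36 | 28-44% |
| 2.5 | 0.29-0.36 | 0.42-0.58 | 29-38% |
| 3 | 0.44-0.50 | 0.57-0.73 | 23-33% |
| 4 | 0.63-0.73 | 0.79-0.90 | 19-20% |
| 5 | 0.78-0.86 | 0.89-0.96 | 11-12% |

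For example, the (5,5,10,30,50) baseline at OR 2 gives (0.341 − 0.190)/0.341 = 44%. The absolute loss runs from 6.5 to 23.7 percentage points.

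**Type I error (OR 1).** Fisher 0.038-0.054, Wilcoxon 0.042-0.053. Both hold the nominal level.

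**Asymptotic cross-check.** Give a 4-df chi-square test the noncentrality (1.96 + z_power)² of a 1-df test. When the 1-df test has 50%, 80% and 90% power, the 4-df test has 31%, 60% and 74%. The relative losses are 38%, 26% and 18%, in line with the simulation.

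**Shifts that are not proportional.** Three assumed patterns reverse the ranking:

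| Pattern | Fisher | Wilcoxon |
|---|---|---|
| Movement out of the top category into the next only | 0.52 | 0.34 |
| Extra low scores | 0.64 | 0.45 |
| Polarised answers | 0.86 | 0.06 |

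**The case against.** The case for leaving the plan alone has real weight.

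- *Fisher's test is valid.* This stands. The error rate is held, so the point concerns efficiency and interpretability. It is also the right test for a truly binary item, which 6.2.3 says the recommend question is. But the form as written does not collect that item as binary.
- *The ranking can reverse.* This stands. A group of very dissatisfied patients in one arm, for instance after failed blocks, could produce a pattern that Fisher's test picks up and a rank test misses. It is the small price of the change. A rank test nevertheless addresses the directional question that a satisfaction comparison normally asks.
- *A Wilcoxon p-value has no effect size either.* True, which is why the estimate and its interval are part of the fix and not an optional extra.
- *The 2x5 table is an inference.* True. The plan does not say whether answers will be collapsed; with no collapsing rule, 2x5 is the plain reading.

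A reader might infer that Fisher's test generally costs a third or more of the available power. The documents supply no distribution or effect size to support that. It describes modest proportional shifts (OR 2 to 2.5), where the rank test itself has only 23-58% power; at OR 4 the loss is about 20%.

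A reader might also infer that a missed difference will be taken as equal satisfaction and used to favour the cheaper regimen. No section says so: satisfaction is not among the objectives in section 2, and section 1.0 leaves cost-benefit analysis to future data. A rank test would often miss a modest difference too.

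**Conclusion.** The point holds as a low-priority improvement. Fisher's exact test is a valid choice for the Likert items, but it discards their order and reports neither direction nor size. For a one-directional shift it loses about 10-45% of the rank test's power in relative terms, assuming proportional odds, odds ratios of 2 to 5 and 36 per arm, with the larger losses at the smaller effects. Under other patterns it may gain. The argument about direction and effect size does not depend on any of these figures.

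The mismatch over the recommend question is a matter of record, not of assumption: 6.2.3 calls it binary, while 4.2.3.1, 5.1 and Appendix E rate it on the Likert scale. Until that is settled, the plan does not fix which items are ordinal. Nothing here affects the primary analysis.

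**What to change.** Replace the test sentence in 6.2.3 with wording to this effect:

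> Each 5-point item will be compared between arms with a two-sided Wilcoxon rank-sum test at the 0.05 level. The difference will be reported as a proportional-odds ratio (or the probability of a better answer in one arm than in the other) with a 95% CI. Binary items will be compared with Fisher's exact test.

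Tabulating the counts in all five categories by arm would let a reader see a polarised pattern that the rank test might miss.

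In the same edit, make 6.2.3, 4.2.3.1, 5.1 and Appendix E agree on how willingness to recommend is recorded. If the form stays as it is, both agreement items are ordinal and take the rank test.

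The cost is a few sentences, settled before the data are unblinded. If the form is kept, no new data are needed, and the sample size is unchanged either way.
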